2.15.6 Analysis of Safety Variables

Safety will be assessed through the degree of pain/discomfort related to the procedure (universal pain scale) and the collection of Adverse Events throughout the course of the study. For each treatment group these variables will be summarized. The summaries will include the number and percent of patients for each outcome. No statistical comparisons will be performed for any of these variables.

3.0 RISK ANALYSIS AND MANAGEMENT

3.1 Risk Determination

This device study used in this study does not meet the FDA definition for a Significant Risk Device study per 21 CFR 812.3(m). Therefore, the sponsor determines that this is a non-significant risk device study.

Significant risk device means an investigational device that:

- (1) Is intended as an implant and presents a potential for serious risk to the health, safety, or welfare of a subject;
- (2) Is purported or represented to be for a use in supporting or sustaining human life and presents a potential for serious risk to the health, safety, or welfare of a subject;
- (3) Is for a use of substantial importance in diagnosing, curing, mitigating, or treating disease, or otherwise preventing impairment of human health and presents a potential for serious risk to the health, safety, or welfare of a subject; or
- (4) Otherwise presents a potential for serious risk to the health, safety, or welfare of a subject.

3.2 Risk Management

The Investigator in this clinical trial has been invited to participate based on his/her previous experience with the use of the system and/or similar systems and industry experience. Experience with treatments is the most critical element in managing subject risk in this trial.

In addition, as with any study, there is a risk of bias. Objective evaluation methods may be used in conjunction with subjective evaluation methods when feasible. The value of the compensation to the clinical investigator for conducting the study is not influenced by the study outcome. If photographic results are listed as the primary objective, they are to be evaluated by blinded evaluators who did not partake in the study. If information concerning investigator assessment of improvement or investigator satisfaction is collected, then it is not listed as an objective for the study.

All other known risks will be disclosed to the subject via the informed consent process. Since this is an elective procedure and the subjects are volunteers, it can be assumed that their signature on the informed consent is indicative of their agreement to accept the risks involved.

The risks to the subjects who participate in this study are the same as those for the subject undergoing similar non-ablative radiofrequency treatment. It is possible to have an adverse reaction to the Elite iQ device use. There may be some side effects that we don't know about yet.

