1.2 Objectives

- 1. Primary Objectives:
 - To assess the safety of the study devices through the collection of side effects throughout the study.
 - To assess efficacy by blinded evaluation of photography.
- 2. Secondary Objectives:
 - To assess of efficacy of the study device through Investigator and subject questionnaires.
 - To assess the ease of use of the new device.

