2.9 Follow Up

- The study subjects are required to return to Investigator site for a follow up evaluation between 30 90 days post last treatment.
- Subject and Investigator questionnaires may be performed at these visits.
- Photographs will be taken, and adverse events will be documented at all follow up visits.
- Some subjects may have an incomplete response or no response by the end of the study. At the end of the study, treatments using an FDA approved/cleared treatment method may be discussed with the subject and obtained at the cost of the subject.

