2.13 Evaluation Methods

Photographs:

Photographs will be taken at all visits and will be used to assess safety and efficacy of treatment.

Treatment Discomfort/Pain Evaluation:

Subjects will be asked to report the general level of treatment discomfort on a scale of 0 (none) to 10 (maximum intolerable pain) using the universal pain assessment tool (Appendix B)

Subject Questionnaire:

The subject will be asked their level of satisfaction using a 6-point Likert scale that ranges from "extremely satisfied" to "extremely unsatisfied."

Subject Satisfaction		
Rating	Description	
6	Extremely Satisfied	
5	Satisfied	
4	Slightly Satisfied	
3	Slightly Unsatisfied	
2	Dissatisfied	
1	Extremely Unsatisfied	

Physician Questionnaire:

The Clinical Global Aesthetic Improvement Scale (CGAIS) ranging from "worse" to "very much improved" will be used to judge the improvement as seen by the treating Investigator.

Global Aesthetic Improvement Scale Assessment		
Rating	Description	
1	Very Much Improved- Optimal cosmetic result in this subject	
2	Much Improved- Marked improvement in appearance form the initial	
condition, but not completely optimal for this subject.		
3	Improved- Obvious improvement in appearance from initial condition, but a re-treatment is indicated.	
4	No Change- The appearance is essentially the same as the original condition.	
5	Worse- The appearance is worse than the original condition.	

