2.15 Statistical Analysis

2.15.1 Hypothesis

For this study to be considered a success, parameters are developed, and the side effect profile is acceptable to the Physician as it relates to this type of treatment.

For secondary objectives to be considered a success, the results from any assessments will need to be statistically significant or have $\geq 80\%$ response rate. In cases where the subject's improvement is being graded on a scale, such as the GAIS scale, we will test the statistical significance of our results against a hypothetical population that would have no change (average score of 4).

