2.15.5 Analysis of Efficacy Variables

The primary efficacy variable is the change from baseline to visit 7 (60 days post last treatment, +/- 30 days) with respect to the indication being treated as evaluated by physician grading with CGAIS. Baseline is defined as the last assessment prior to the first treatment. The change from baseline to visit 13 will be analyzed using a Mixed Model Repeated Measures Analysis of Variance. A pairwise treatment group comparison at visit 7 will be performed using the results of this analysis. If a patient has no post-baseline assessment of the primary efficacy variable the patient data will be excluded from the statistical analysis of the improvement. Statistical

significance with respect to the treatment group comparison at visit 7 will be declared if the two-sided p-value is < 0.05. For each treatment group summaries will be prepared for both the observed assessment and the change from baseline. Subject satisfaction results from Visits 12 and 13 will also be included in the summary. The summaries will include the sample size, mean, median, standard deviation, minimum, and maximum. Categorical variables will also include a summary which will include the number and percent of patients for each outcome. The statistical significance of the mean change from baseline for each treatment group will be determined using a student's paired t-test.

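### Section 3.2 bars investigator-rated improvement from the objectives, but 1.2 lists it, 2.15.1 lets it count as success and 2.15.5 makes it the primary efficacy variable

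*Combined protocol and SAP*

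**What the plan says.** Section 3.2 (Risk Management) acknowledges a risk of bias and lists several measures against it: objective methods where feasible, investigator compensation unrelated to outcome, and blinded evaluators for photographs when these are a primary objective. It then adds: "If information concerning investigator assessment of improvement or investigator satisfaction is collected, then it is not listed as an objective for the study".

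Four other parts of the protocol bear on that sentence.

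- **1.2 Objectives.** A secondary objective reads "To assess of efficacy of the study device through Investigator and subject questionnaires". Blinded evaluation of photographs is a primary objective.
- **2.12 and 2.13.** The schedule marks the investigator questionnaire at Visit 7. Section 2.13 defines the physician questionnaire as the CGAIS, which "will be used to judge the improvement as seen by the treating Investigator". The scale runs from 1 (best) through 4 (no change) to 5 (worse).
- **2.15.1 Hypothesis.** "For secondary objectives to be considered a success, the results from any assessments will need to be statistically significant or have" a response rate of at least 80%. For graded scales, "such as the GAIS scale, we will test the statistical significance of our results" against a no-change mean of 4.
- **2.15.5 Efficacy.** "The primary efficacy variable is the change from baseline to visit 7", as graded by the physician on the CGAIS, with significance at a two-sided p below 0.05.

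**The concern.** The study is open label (2.2), so the treating investigator knows that every subject was treated. The test in 2.15.1 compares the grades with a fixed value of 4. Although 2.15 mentions treatment groups, the design sections (2.1 and 2.2) describe no control arm. No concurrent group would therefore absorb a lenient rater, and any favourable tendency in the grading passes straight into the test statistic.

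Section 3.2 appears to guard against this by keeping the rating out of the objectives. Someone relying on 3.2 would take that protection to be in force. Someone following 1.2, 2.15.1 and 2.15.5 would use the same unmasked grade to support an efficacy claim.

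**Working it through.** **Step 1: is the condition in 3.2 met?** The sentence applies only if the rating is collected. Section 2.9 is permissive: "Subject and Investigator questionnaires may be performed at these visits". The schedule in 2.12 nevertheless marks the investigator questionnaire at Visit 7, 2.13 specifies its scale and rater, and 2.15.5 analyses it. Collection is planned.

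**Step 2: does the rating fall under the rule?** Section 3.2 refers to investigator assessment of improvement. The CGAIS in 2.13 is the treating investigator's judgement of improvement. It falls under the rule.

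**Step 3: is the rule kept?**

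| Section | Role of the investigator's rating | Consistent with 3.2? |
|---|---|---|
| 3.2 | Not an objective if collected | (the rule) |
| 1.2 | Part of a secondary efficacy objective | No |
| 2.15.1 | Can make a secondary objective succeed | No |
| 2.15.5 | Primary efficacy variable | No |

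Correcting 2.15.5 alone would leave 1.2 and 2.15.1 in conflict with 3.2. Correcting 1.2 and 2.15.1 alone would leave the rating as primary efficacy variable.

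**Step 4: how much could a lenient rating matter?** The plan gives no figure to reproduce, so this is an illustration.

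Inputs from the plan:
- null mean of 4 (2.15.1);
- two-sided 0.05 (stated in 2.15.5; 2.15.1 gives no level);
- 20 subjects, including departures (2.15.2);
- exclusion from the improvement analysis of subjects with no post-baseline assessment (2.15.5).

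Assumptions:
- a one-sample t-test, since 2.15.1 names no test;
- a device with no effect;
- an SD of 0.75, 1 or 1.25 grades;
- a favourable rating shift of 0.25 or 0.5 grade, so that the mean grade is 3.75 or 3.5;
- 12, 16 or 20 evaluable subjects.

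Formula: the probability of significance in the favourable direction is P(T > t(0.975, n−1)), where T is noncentral t with n−1 degrees of freedom and noncentrality (shift/SD) × √n.

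Example: n = 20, SD 1, shift 0.25. Noncentrality is 0.25 × √20 = 1.118, the critical value is 2.093, and the probability is 0.185. With shift 0.5, noncentrality is 2.236 and the probability is about 0.56.

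| n | SD | Shift 0.25 | Shift 0.5 |
|---|---|---|---|
| 12 | 0.75 | 18% | 56% |
| 12 | 1 | 12% | 35% |
| 12 | 1.25 | 9% | 24% |
| 16 | 1 | 15% | 46% |
| 20 | 0.75 | 29% | 81% |
| 20 | 1 | 18% | 56% |
| 20 | 1.25 | 13% | 40% |

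With no shift the figure is 2.5%. The alternative route, a response rate of at least 80%, is not calculated because the plan does not define a responder on the CGAIS.

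**The case against.** The strongest reply is that an investigator-rated secondary endpoint is a legitimate choice in an open-label device study, and that 3.2 may mean only to keep it from being the primary objective. The first half stands: whether to use such an endpoint is the sponsor's decision, and the defect is that the sections disagree. The second half does not. Section 3.2 speaks of an objective without qualification, although its preceding sentence does say primary objective when it deals with photographs. Even on the narrower reading, 2.15.5 conflicts in substance, because it gives the physician's CGAIS the primary efficacy role.

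Some stronger inferences are tempting, and the documents do not support them.

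- *Bias protection fails altogether.* Only one sentence of 3.2 is contradicted. Blinded photograph evaluation is a primary objective in 1.2, and the statement on compensation is unaffected.
- *A lenient grader could make the study succeed.* Under 2.15.1, study success rests on parameters being developed and a side-effect profile acceptable to the physician. The GAIS test belongs to the separate clause on secondary objectives.
- *The rater also sets the treatment, and 3.2 promises protection from that.* Section 2.7 allows parameters to be adjusted and 1 to 5 treatments per area, but does not say who decides. It may well be the treating investigator, but that is inference, and 3.2 does not address it.

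The numerical illustration is also open to challenge. Neither the SD nor the shift has a source in the plan, and fewer evaluable subjects lower the percentages. This is why a range is shown.

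**Conclusion.** The contradiction is established from the text and does not depend on any calculation. The plan collects investigator-rated improvement, lists it as part of a secondary efficacy objective, lets it count as success, and names it the primary efficacy variable, while 3.2 says it is not an objective. Nothing elsewhere in the document reconciles these statements.

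The consequence is confined to efficacy claims. Under the assumptions above, an ineffective device would reach favourable significance in roughly 9% to 29% of studies with a 0.25-grade shift and 24% to 81% with a 0.5-grade shift. These figures show that modest leniency could matter. They do not estimate the bias in this study, which the documents give no means of sizing. The point should be corrected because it governs how efficacy may be claimed.

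**What to change.** Reconcile 1.2, 2.15.1, 2.15.5 and 3.2 in one amendment, applying 3.2 as it stands:

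1. In 1.2, remove the investigator questionnaire from the secondary efficacy objective and keep the subject questionnaire.
2. In 2.15.1, take the treating investigator's CGAIS out of the success test, including the response-rate route.
3. In 2.15.5, replace physician-graded CGAIS as the primary efficacy variable with the blinded photograph evaluation already named in 1.2.
4. Report the investigator's CGAIS descriptively, labelled as unmasked grading by the treating investigator.
5. In 2.13 and 2.15, specify the scale and analysis for the blinded photograph reading.

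If the sponsor prefers to keep the investigator's rating as an objective, the sentence in 3.2 must be changed to say that this safeguard is not used, and the result labelled as unmasked. The mismatch between 1.2 and 2.15.5 over the primary efficacy measure would still need correcting.

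The cost is more than a few deleted words. The formal test of the investigator's CGAIS is lost, and CGAIS is the only improvement scale the plan defines. The photograph reading currently has no scale or analysis, so both must be written; otherwise no defined test of improvement remains. No extra reader is needed, because blinded evaluators are already planned, and no visits or subjects are added.

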3.3 Risk Analysis

CONTEXT OF THE PROPOSED INVESTIGATION:

The Alexandrite wavelength (755 nm) and the Nd:YAG wavelength (1064 nm) target hair follicles, unwanted veins, pigmented lesions and treat sun-damaged skin. The Elite iQ laser system delivers the correct combination of wavelengths (755 and 1064 nm), high fluences (up to 600 J/cm2) and long pulses (up to 300 ms) for its clinical applications. Further investigation of parameter optimization is necessary to achieve safe and efficacious results.

ASSESSMENT OF RISKS OF THE PROPOSED INVESTIGATION:

There is one risk identified with the Elite iQ device used in this study. The risk identified is the lack of clinical data using this software for evidence of effectiveness. Parameters need to be further investigated to be optimized for efficacious results.

The risk identified with the overall clinical investigation is the integrity of the data collected.

There are multiple clinical mitigation strategies for the risks identified. Proper training on the device and protocol will be performed. Data from prior investigations will be utilized to minimize side effects and optimize treatment outcomes. Monitoring of the study will be implemented to minimize subject and data risks.

ASSESSMENT OF BENEFITS OF THE PROPOSED INVESTIGATION:

The subject may or may not have improvement for the indication treated.

CONSIDERATION OF PATIENT PREFERENCE INFORMATION:

Many physicians support the use of laser devices for non-invasive cosmetic treatments due to current patient satisfaction of cosmetic results with the currently available devices. However, there is still a level of interest in novel technologies that could reduce the need for future treatments with better treatment outcomes.

ASSESSMENT OF UNCERTAINTY:

There is uncertainty of the efficacy of the treatment with the use of the Elite iQ system.

CONCLUSION:

The Elite iQ device is determined to be a non-significant risk study and has been FDA cleared for use. This device poses similar risks to its predicate device, the Elite+, which is also currently FDA cleared for use. The risks posed to the subjects and integrity of data are acceptable.

Patient population to be enrolled in this clinical study:

Total anticipated population: 20 Subjects Age Range: 18 years of age or older

Gender: Male or Female

Condition: Hair removal and benign vascular and pigmented lesions.

4.0 DEVICE DESCRIPTION AND SPECIFICATIONS

On March 9th, 2020, the Elite iQ device used in this study was cleared for use by the U.S. Food and Drug Administration (the FDA) under K193426 for the following indications:

755nm:

The Elite iQ Laser System is indicated for stable long-term or permanent hair reduction. Permanent hair reduction is defined as long-term stable reduction in the number of hairs regrowing when measured at 6, 9 or 12 months after the completion of a treatment regime. It is used for skin types (Fitzpatrick I-VI) including tanned skin. It is also indicated for the treatment of vascular lesi ons, benign pigmented lesions, and wrinkles.

1064nm:

The Elite iQ Laser System is intended for the coagulation and hemostasis of benign vascular lesions such as, but not limited to, port wine stains, hemangiomas, warts, telangiectasia, rosacea, venous lakes, leg vein s, spider veins and poikiloderma of Civatte; and treatment of benign cutaneous lesions such as warts, scars, striae and psoriasis. The laser is also intended for the treatment of benign pigmented lesions such as, but not limited to, lentigines (age spots), solar lentigines (sunsp ots), cafe au lait macules, seborrheic keratoses, nevi, chloasma, ver rucae, skin tags, keratosis and plaques.

The laser is also indicated for the treatment of wrinkles such as, but not limited to, periocular and perioral wrinkles.

Additionally, the laser is indicated for the treatment of pseudo folliculitis barbae (PFB) and for stable long-term or permanent hair reduction. Permanent hair reduction is defined as long-term stable reduction in the number of hairs regrowing when measured at 6, 9 and 12 months after the completion of a treatment regime.

The Skintel Reader is intended as an objective measurement tool for examining skin melanin content for determining and setting a test spot starting fluence

The Elite iQ Device Specifications are:

Specification	Alexandrite (755nm) For Both the M122B1 and	Nd:YAG (1064nm) For the M122B1 Model Only
Wavelength	M122D1 Models 755 nm +10/-5 nm	1064 nm ± 1.0 nm
Pulse Width	≤300 ms (max discrepancy -2%)	≤300 ms (max discrepancy -2%)
		. , , ,
System Cooling Method	Water (internally circulated with hea	at exchanger to air)
Mode of Operation	On/Off: 3 min/5 min	
Nominal Ocular Hazard Distance (NOHD)	448m	239.5m
Protective Eyewear Specification for diffuse viewing, 300mm distance, 5s exposure time	OD≥4 DLB5 ILB7 @755nm	OD≥4 DLB5 ILB7 @1064nm
Fluence Incident on Eyewear Surface for Diffuse Viewing Resistance Determination	0.3 J/cm ²	0.5 J/cm ²
Protective Eyewear Specification for direct intra-beam viewing, 100mm distance, 5s exposure time*	OD≥6 DLB7 ILB9 @755nm	OD>6 DLB7 ILB9 @1064nm
Fluence Incident on Eyewear surface for intra-beam resistance determination	104.3 J/cm ²	156.5 J/cm ²
Corneal Maximum Permissible Exposure (MPE)	77.54mJ/m²	254.6mJ/m ²
Optical Density (min)	OD≥6	OD≥6
Maximum Output Power (from handpiece)	106 W ±20%	154 W ±20%
Maximum Output Energy (from handpiece)	63.5 J	91.2 J
Aiming Beam Source/Wavelength	Diode laser, 532 nm, green Selectable intensity between 1% and 100%	
Aiming Beam Max. Delivered Output Power	4.0 mW	

Changes to the Elite iQ device are not anticipated during the investigation.

5.0 MONITORING PROCEDURES

The Sponsor Standard Operating Procedure (SOP) for monitoring the investigative site will be followed. The sponsor will train the site following sponsor SOP's and may be present at initiation of treatment. The sponsor will also monitor the site periodically. The Investigator/Institution will permit trial-related monitoring, audits, IRB/IEC review, and regulatory inspections by providing direct access to source documents. The sponsor may request intermediate data following each visit to evaluate treatment progress. Case Report Forms will be reviewed for current data and Regulatory Binders will also be reviewed for correct documents. The sponsor will collect data at

the end of the follow up period. The sponsor will list the study on clinicaltrials.gov when required by FDA regulations.

The monitoring plan for this study is outlined in the Cynosure Monitoring Plan.

ASSIGNED CLINICAL RESEARCH MONITOR:

Monitor #1

Name: [name]

Institution: Cynosure, LLC

Address: [name]

6.0 LABELING

Sample labeling will follow FDA regulations and the sponsor standard operating procedure. If applicable, the Elite iQ device label will include, (in accordance with 801.1):

Statement: "CAUTION--Investigational device. Limited by Federal (or United States) law to investigational use."

Additionally, the label or other labeling will describe all relevant contraindications, hazards, adverse effects, interfering substances or devices, warnings, and precautions.

Directions for use are contained in the Elite iQ Operator's Manual

7.0 CONSENT MATERIALS

Forms and informational materials which are provided to the subject during the informed consent process are listed below:

Form/Informational Material Description
Pre and Post Treatment Instructions
Informed Consent Form

8.0 INSTITUTIONAL REVIEW BOARD INFORMATION

This protocol, informed consent forms, and any amendments to the protocol will be reviewed by the appropriate Institutional Review Board prior to initiation. The study will not be initiated without the approval from the Institutional Review Board.

